4.5 Randomization Methods

Allocation to the study groups will be randomly assigned using a web-based randomization tool as part of Research Electronic Data Capture (REDCap). The randomization sequence was generated using randomly permuted blocks of 4, 6, and 8 with a 1:1 allocation ratio.

4.6 Masking:

Trial participants are masked to treatment group allocation. All health care providers involved in care of the trial participants including physicians, surgeons, and nurses are masked to treatment group allocation. Research team members including research coordinators, data collectors, and data analysts, are masked to treatment group allocation.

Masking is established and maintained by preparation of the study solutions in visually indistinguishable syringes labeled either “Solution A” or “Solution B”.

Two UCSF research personnel are unmasked for the implementation and management of trial protocols, but do not have any contact with study participants and are not aware of the treatment group to which each participant is assigned. The study nurse responsible for preparation of study solutions at MOI is also unmasked, but does not have any contact with study participants and is not aware of the treatment group to which each participant is assigned.

4.7 Description of Interventions

4.7.1 Study Solution Preparation and Storage

A certified study nurse, who is one of three un-masked personnel, will prepare aqueous gentamicin and normal saline solutions. The gentamicin solution consists of 2mg/mL aqueous gentamicin while the control solution consists of normal saline without active agent.

The working solutions are prepared in a locked room using sterile technique and are prepared in identical syringes labeled either “Solution A” or “Solution B”, according to the masking key. The masking key is kept in a locked cabinet in a locked office, only accessible by the study nurse. Solutions are labeled with date of preparation and date of expiration. The study nurse maintains a preparation log to ensure the integrity of the study solutions.

Study solutions are stored at 4 degrees Celsius for up to 48 hours, in accordance with pharmacist guidelines. Solutions are stored in a locked, dedicated study refrigerator adjacent to the operating suite. Upon expiration, unused study solutions are discarded and new solutions prepared. The study refrigerator is checked daily by the study nurse and a use log is maintained to ensure the integrity of the study solutions. All gentamicin is obtained from Sichuan Long March Pharmaceutical Co., Ltd (Leshan, Sichuan Province, China) and normal saline is obtained from Otsuka Pharmaceutical India Private Limited (Ahmedabad, India).

4.7.2 Study Solution Administration

Following intraoperative randomization, the appropriate study solution is provided to the administering surgeon in a masked manner. The local solution injection is administered immediately following wound closure. As described previously by Lawing et al¹⁹, the solution is injected by inserting a 22-gauge needle down to bone through an anteromedial approach at the level of the fracture site such that the injected solution fills the wound cavity. A minimum of 5mL of study solution may be injected, and the injection is continued until either extravasation is seen through the traumatic wound or a maximum of 40mL has been administered, whichever occurs first.

For quality control, the efficacy of masked study solutions will be tested against standard organisms. This will occur once per month for the first 6 months and once every 3 months thereafter by the Muhimbili University of Health and Allied Sciences (MUHAS) microbiology lab, with results evaluated by unmasked study personnel.

4.7.3 Perioperative Co-Interventions

Systemic antibiotic prophylaxis

All patients will receive prophylactic systemic antibiotics as soon as possible after presentation to the hospital regardless of whether they participate in the study. Patients will be given a single dose of ceftriaxone 1 gram intravenously, which provides 24 hours of coverage.

Debridement

All patients will undergo systematic debridement of the traumatic wound with removal of devitalized bone and soft-tissue. Wounds will be extended as necessary to remove contaminants and deliver the bone ends from the wound. The wound will be irrigated with a minimum of 2 liters normal saline solution using low-pressure lavage. For cases of severe contamination, the wound may be washed with tap water prior to surgical prep.

Fracture stabilization

Treatment of the fracture will be at surgeon discretion and may be temporizing or definitive using either external fixation (EF) or intramedullary nailing (IMN).

External fixator: A uniplanar external fixator (AO Dispofix) will be used in all cases consisting of a minimum of two Schanz pins proximal to the fracture and two distal pins connected by a single stainless steel bar. The choice to add additional pins or span adjacent joints will be at the discretion of the treating surgeon. At hospital discharge, the patient will be instructed on proper pin-care procedures. The pin care protocol will consist of cleaning each pin using methylated spirits (methyl alcohol) twice daily until the external fixator is removed. The external fixator will remain in place for a minimum of 4-6 weeks and maximum of 3 months.

Intramedullary Nail: The SIGN Standard nail (SIGN Fracture Care International, Richland, WA) will be used in all cases. The nail will be inserted using an infrapatellar approach. Two proximal and two distal interlocking screws will be placed using an external jig. Intraoperative fluoroscopy will not be used.

Wound closure

The wound will be closed primarily when it is felt to be safe and feasible by the treating surgeon. A layered closure will be performed whenever possible using nylon for skin and a braided absorbable suture for the deeper layers.

Postoperative Wound Care

If the wound is dry at the 2-week wound check, the dressing will be removed. If the wound is still wet at 2 weeks, the dressing will be changed and the patient will be instructed to periodically revisit the hospital to change the dressing until the wound becomes dry.

Weight Bearing Protocol

All patients will be advised to be on toe-touch status for the first 6 weeks. Afterwards, the patient will be instructed to bear weight as permitted by pain.

4.6 Description of Data Collection

4.6.1 Data collection

Three trained research coordinators with research and data collection experience will be responsible for all data collection. All data will be uploaded into REDCap (see section **6.0 DATA MANAGEMENT**) using portable laptops and tablet computers.

4.6.2 Overview of Data Collection Instruments

Data will be collected in the schedule described in section 4.4 Schedule of Events, and includes:

- Baseline patient data includes demographic information, such as age, gender, medical history, and injury characteristics.
- The EuroQol-5 Dimensions, 3-level questionnaire (EQ-5D)²⁰, Swahili version, which is a validated instrument for measuring patient quality of life.
- The Function Index for Trauma (FIX-IT)²¹, a validated instrument for evaluating healing in lower-extremity fractures. The scoring system includes a single-leg stand, ambulation, and palpation test.
- The Modified Radiographic Union Score for Tibia (mRUST)²² is a validated, radiographic measure of bony union.

4.6.3 Wound Measurement and Classification

Wound Measurement and Classification

A measurement of the wound is to be done in the operating room, both before and after debridement. The first measurement will be taken prior to debridement. The second measurement will be taken following surgical fixation but before wound closure. The wound should be measured using a centimeter ruler or the handle of a scalpel (rather than visually approximated).

Only the maximum dimension of the wound (the longest length possible) needs to be recorded. This is irrespective of how the wound is oriented along the limb. The wound length should only include the part of the wound that is open (ignore any superficial abrasions that may be connected to the open part of the wound). In the event that there are multiple wounds, measure each wound that communicates with the fracture and sum the lengths of the individual wounds. *Do not* include the wounds that were made for the purpose of inserting an intramedullary nail or interlocking screws.

OTA and Gustilo-Anderson Wound Classification

Classification of the wound is done using the OTA Wound Classification questionnaire and the Gustilo-Anderson classification of injury severity. Wound classification is to be done after surgical debridement, which allows the surgeon to fully assess the wound.

4.6.4 Radiographs

Orthogonal images will be obtained and digitally copied using screen capture. Images will then be uploaded into REDCap. Radiographs are then sent for review by the adjudication committee, and are assessed for radiographic signs of healing using the mRUST score by two fellowship-trained orthopaedic trauma surgeons. In cases of disagreement between reviewers, decisions are made by consensus.

4.6.5 Economic Analysis

Indirect Cost Assessment

Lost productivity will be assessed using the Work Productivity and Activity Impairment (WPAI) survey modified for lower extremity injury. Employment type, hours worked, and wages earned will be assessed at each time point. Transportation costs associated with the injury and follow up care will be assessed at each time point.

Direct Cost Assessment

Direct costs will be measured using micro-costing methods. Resource utilization and time data will be collected through direct observation using time and motion (TM) analysis and patient charts. Specifically, each of the captured surgical interventions (each treatment strategy as well as reoperation for complication) is divided into discrete steps. For each step, resources used, personnel involved and duration of activity will be directly observed and recorded. This information will be used to assess personnel costs of each surgical procedure. Implant costs will be obtained from the suppliers. Surgical instrument costs will be obtained from the manufacturers, accounting for depreciation by assuming that the lifetime of surgical instruments is 10 years. The cost of intraoperative supplies, such as medications, disposables, intravenous fluids, blood products, and others, will be obtained from the suppliers.

Cost per day of hospital stay will be estimated for three categories: index hospitalization, infected complication hospitalization, and uninfected complication hospitalization. This is based on the assumption that the cost per day of hospital stay will differ between these groups but not significantly within these groups.

Utilization of medications and laboratory and radiology investigations will be assessed from the patient chart. Type and quantity of medications will be obtained from the patient chart, and costs will be obtained from the supplier. Labor and resource costs of laboratory and radiology interventions will be obtained from the hospital laboratory and radiology departments.

4.7 Outcome Measures

4.7.1 Feasibility Trial Outcomes

7. Recruitment: number of patients screened, number and proportion of patients screened that are eligible, enrolled, randomized, and receive intervention.
8. Retention: number and proportion of randomized patients who attend each follow-up visit. We aim for an adherence rate at follow-up of 80% at one year, which was achieved in our previous open tibia fracture trial performed through the same collaborative partnership.
9. Data collection completeness: proportion of fracture-related infection criteria, EuroQol-5 Dimensions, 3-level questionnaire (EQ-5D), Function Index for Trauma (FIX-IT), and

Modified Radiographic Union Score for Tibia (mRUST)¹⁷ indices complete at each time-point.

10. Solution quality control: confirmation of the ongoing sensitivity of standard organisms to trial solutions via interval testing. This will occur once per month for the first 6 months and once every 6 months thereafter by the Muhimbili University of Health and Allied Sciences (MUHAS) microbiology lab, with results evaluated by unmasked study personnel.
11. Masking and concealment: determination of the continued masking of surgeons to solution identity via intraoperative surgeon survey.
12. Evaluation of primary and secondary outcomes: reliability of fracture-related infection and mRUST scoring, validation of telephone criteria for fracture-related infection, radiographic image quality, and completeness of EQ-5D and FIX-IT.

4.7.2 Definitive Trial Outcomes

Primary Outcome

The primary outcome is occurrence of *fracture-related infection* (FRI) a binary variable. FRI diagnosis is likely to peak between 3 and 6 months after surgery and has a non-normal time-to-event distribution, with incident cases rarely presenting later than 12 months after surgery. Any of the four following diagnostic criteria are confirmatory for infection: (1) fistula, sinus or wound breakdown; (2) purulent drainage from the wound or presence of pus during surgery; (3) phenotypically indistinguishable pathogens identified by culture from at least two separate deep tissue/implant specimens; or (4) presence of microorganisms in deep tissue taken during an operative intervention, as seen on histopathological examination.

Secondary Outcomes

The following secondary outcomes will be assessed:

1. Occurrence of nonunion, a binary variable, as defined by:
 - a. Any unplanned reoperation for promotion of bone healing; OR
 - b. mRUST ≤ 10 AND either: FIX-IT score ≤ 11 at 12 month follow-up, OR recommendation by treating surgeon for nonunion repair surgery.
2. Occurrence of unplanned fracture-related reoperation, a binary variable, for infection, wound healing, or fracture union, excluding removal of implants for prominence/irritation. This may include but is not limited to:
 - a. Irrigation and debridement of surgical incisions or open fracture wounds due to infections or wound healing problems;
 - b. Revision wound closure for dehiscence;
 - c. Soft tissue coverage procedure for infected or necrotic wound;
 - d. Fracture delayed union or nonunion surgery (such as bone grafting or implant exchange);

- e. Reoperation for hardware or prosthesis failure due to infection or bone-healing problems;
- f. Amputation for infection, wound or fracture healing problem.

Subsidiary Outcomes

The following subsidiary outcomes will be assessed:

1. Radiographic healing via the mRUST score, an ordinal scale ranging from 4 to 16.
2. Clinical healing via the FIX-IT score, an ordinal scale from 0-12 that encompasses two domains, ability to weight-bear and pain at fracture site, each scored from 0-6: ability to weight-bear and pain at fracture site.
3. Health-related quality of life via EQ-5D.
4. FRI suggestive criteria, including clinical (wound redness, fever) and radiographic signs (sequestrum), elevated serum inflammatory markers, and new onset or increased wound drainage.
5. C-reactive protein level, including preoperative level and postoperative level collected over longitudinal time points
6. Direct and indirect costs as measured by Time and Motion analysis and WPAI

Subgroup Analyses

In order to examine the differential treatment effects of local gentamicin administration among clinically relevant subgroups defined by: i) GA classification, ii) severity of wound contamination, iii) time from injury to surgery, and iv) type of definitive fixation, the following subgroup analyses will be performed:

1. Gustilo-Anderson classification of fracture (type 1 or 2 vs 3)
2. Contamination (minimal or moderate versus severe based on the Orthopaedic Trauma Association Open Fracture Classification)
3. Time to surgery (≤ 24 versus > 24 hours after injury)
4. Type of fixation (external fixation versus intramedullary nailing).

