Diagnosis and Main Inclusion Criteria	All patients 18 years of age or older who present to Muhimbili Orthopaedic Institute (MOI) for treatment of Gustilo-Anderson (GA) Type I, II or IIIA open tibia fractures will be screened for participation. Eligible patients must present to the hospital within 48 hours of their injury and receive surgical debridement of their open fracture wound within 7 days of their injury. The open wound must be primarily closable at the index debridement.
Treatment Groups	The pGO-Tibia trial will compare two solutions: 1) aqueous gentamicin solution (2mg/mL) in normal saline, or 2) normal saline only. A minimum of 5mL and a maximum of 40 mL of either solution will be injected into the fracture site immediately following primary closure of the traumatic wound.

Randomization	Allocation to the study groups will be performed using a web-based randomization. The randomization sequence was generated using randomly permuted blocks of 4, 6, and 8 with a 1:1 allocation ratio.
Study Outcomes	The definitive trial primary outcome is occurrence of FRI. Secondary outcomes of the definitive trial are the occurrence of 1) nonunion, and 2) unplanned fracture-related reoperation within 12 months of definitive fixation. Definitive trial subsidiary outcomes include health-related quality of life, radiographic healing, and clinical healing. A blinded adjudication process will judge each study event on occurrence of FRIs, nonunions, and unplanned fracture-related reoperations.
Feasibility Outcomes	This pilot trial will focus on the following feasibility endpoints: Recruitment: number of patients screened, number and proportion of patients screened that are eligible, enrolled, randomized, and receive intervention. Retention: number and proportion of randomized patients who attend each follow-up visit. Data collection completeness, solution quality control, masking and concealment, and evaluation of primary and secondary outcomes (reliability of fracture-related infection and mRUST scoring, radiographic image quality, and completeness of EQ-5D and FIX-IT).
Follow-Up	Study participants will be followed at 2 weeks, 6 weeks, 3 months, 6 months, 9 months, and 12 months from their fracture.
Sample Size	50 individuals per arm will be included in the feasibility trial.

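### FRI criterion 1 counts any wound breakdown as confirmed infection, without requiring depth, communication with the fracture or implant, or evidence of infection

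*Combined protocol and SAP*

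**What the plan says.** All references are to the combined protocol and SAP.

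- **Primary outcome (Section 4.7.2, Definitive Trial Outcomes).** FRI is a yes/no variable, and one criterion is enough: "Any of the four following diagnostic criteria are confirmatory for infection: (1) fistula, sinus or wound breakdown". Criterion 2 is pus. Criterion 3 asks for "phenotypically indistinguishable pathogens identified by culture from at least two separate deep tissue/implant specimens". Criterion 4 asks for "presence of microorganisms in deep tissue taken during an operative intervention", seen on histopathology.
- **Reoperation outcome (same section).** It covers unplanned surgery "for infection, wound healing, or fracture union, excluding removal of implants for prominence/irritation". Item 2a reads "Irrigation and debridement of surgical incisions or open fracture wounds due to infections or wound healing problems", and item 2b, standing alone, reads "Revision wound closure for dehiscence".
- **Costs (Section 4.6.5, Economic Analysis).** Hospital days are costed in three groups: "index hospitalization, infected complication hospitalization, and uninfected complication hospitalization".
- **Adjudication.** The Study Summary states: "A blinded adjudication process will judge each study event on occurrence of FRIs, nonunions, and unplanned fracture-related reoperations". Section 4.7.3 (Steering Committee and Adjudication) lists only two kinds of event for review: deaths, and surgical complications that need a reoperation. Three members vote on whether the event is a primary outcome.
- **Planning (Section 5.1).** The sample size rests on a 12% rate of deep infection, halved by treatment.

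**The concern.** Criterion 1 is the only one of the four that can be met without pus, a matching deep culture or organisms in deep tissue. A wound edge that separates for mechanical reasons, with no sign of infection, satisfies it. Elsewhere the protocol recognises that wounds can fail, and complications can occur, without infection, but it never says how an uninfected dehiscence is to be scored for FRI.

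If such cases occur at similar rates in both arms, they pull the relative effect towards no difference. They also raise the FRI rate above the deep-infection rate used for planning. This matters already in the pilot. Section 2.0 says that the pilot will supply effect sizes for the definitive trial's power calculation, and Section 4.7.1 (Feasibility Trial Outcomes) makes the reliability of FRI scoring and the validation of telephone FRI criteria feasibility outcomes. All three depend on what criterion 1 means.

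**Working it through.** **Step 1. What each criterion requires (Section 4.7.2).**

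| Criterion | Depth required? | Evidence of infection required? |
|---|---|---|
| 1. Fistula, sinus or wound breakdown | No | None for breakdown |
| 2. Pus from the wound or at surgery | No | Yes, pus |
| 3. Matching cultures | Yes, deep tissue or implant | Yes, two specimens |
| 4. Histopathology | Yes, deep tissue | Yes, organisms seen |

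The suggestive tier in the same section includes redness, fever, sequestrum and new or increased drainage. Breakdown with none of these is still confirmatory.

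**Step 2. Does adjudication remove uninfected breakdown?** A breakdown managed without surgery is not on the review list in Section 4.7.3. A breakdown that leads to reoperation is on the list, but the members are given no rule for voting no on an event that meets criterion 1. The Summary's wider promise is not carried into the procedure.

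**Step 3. Reproduce the plan's figure (Section 5.1).** Inputs: 12% v 6%, two-sided alpha 0.05, power 0.80, 1:1 allocation, 20% loss. The pooled two-proportion formula, with p̄ the mean of p1 and p2, is

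n = [1.960·√(2p̄(1−p̄)) + 0.8416·√(p1(1−p1)+p2(1−p2))]² / (p1−p2)²

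= [1.960·√0.1638 + 0.8416·√0.1620]² / 0.06² = (0.7932 + 0.3387)² / 0.0036 ≈ 355.9.

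This rounds up to 356 per arm, or 712 in all, and 712/0.80 = 890. The plan's figures are matched exactly.

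**Step 4. Illustrate the dilution.** Assume that uninfected breakdown adds b points to both arms, on top of 12% v 6%, and that gentamicin has no effect on it. The documents give no value for b. Power at n = 356 is

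Φ{[0.06·√356 − 1.960·√(2p̄(1−p̄))] / √(p1(1−p1)+p2(1−p2))}.

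For b = 2: p1 = 0.14, p2 = 0.08, p̄ = 0.11, giving (1.1321 − 0.8673)/0.4405 = 0.601 and Φ = 0.726.

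| b (points) | Rates | Risk ratio | Power at 356 per arm |
|---|---|---|---|
| 0 | 12% v 6% | 0.50 | 80.0% |
| 2 | 14% v 8% | 0.57 | 72.6% |
| 4 | 16% v 10% | 0.625 | 66.3% |
| 6 | 18% v 12% | 0.67 | 61.1% |

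The risk difference stays at 6 points throughout; the ratio and the variance change. The risk ratio stands in here for the planned relative hazard, because Section 5.1 sizes the trial on risks.

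**Step 5. The same question with the control rate held at 12%.** Suppose instead that a share f of the 12% is uninfected breakdown, unaffected by treatment. The treated rate is then 12%·f + 6%·(1−f). For f = 10% this is 6.6% and power is 69.9%; for f = 20% it is 7.2% and power is 58.5%. The documents give no value for f either.

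**Step 6. Pilot scale.** With 50 per arm and no loss, 12% v 6% means 6 v 3 expected events (50 × 0.12 and 50 × 0.06). Adding 2, 4 or 6 points means 1, 2 or 3 more patients per arm.

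**The case against.** The strongest reply has five parts.

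1. **The reoperation list gives reasons for surgery; it does not classify infection.** This stands. The two outcomes may overlap, and wound-healing problems are wider than breakdown: item 2c includes a necrotic wound. A reader might infer that criterion 1 contradicts the reoperation outcome or empties its wound-healing category. The documents do not support that.
2. **The two tiers look deliberate.** Breakdown was placed with pus in the confirmatory tier, and redness and drainage were placed below. That may be so, but a deliberate broad criterion still needs a rule for uninfected dehiscence, and none is given.
3. **Adjudication is a safeguard.** It is in part. Dehiscence that leads to reoperation would be seen by three members, but Step 2 shows the gaps.
4. **Nothing shows that gentamicin would leave breakdown unchanged.** This stands. Section 1.1 calls open fractures contaminated, so some breakdown may reflect infection. Section 1.3 cites a retrospective cohort with lower odds of deep and superficial infection together. Equal addition to both arms is an assumption.
5. **This is a 100-patient feasibility pilot.** This stands as to scale. Section 5.2 describes the outcome methods mainly for planning and expects them to be revised on pilot data.

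**Conclusion.** The point holds as an over-inclusive definition that should be tightened. As written, criterion 1 scores an uninfected, superficial wound breakdown as confirmed FRI, and the adjudication procedure does not reliably correct this.

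The size cannot be fixed from the documents. The fall in power from 80% to between 73% and 61% rests on three assumptions: an assumed 2 to 6 points of uninfected breakdown, no treatment effect on it, and all of it being additional to the planned 12% v 6%. If it is absent, nothing changes.

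A reader might infer that the definitive trial is underpowered or wrongly sized. The documents do not support that: the arithmetic of Section 5.1 is correct, and that section does not say how the earlier trial defined deep infection, so the overlap with criterion 1 is unknown. For this pilot, the consequence is limited to the reliability of FRI scoring and the FRI rate and effect size carried forward.

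**What to change.** 1. Reword criterion 1 to: *fistula, sinus, or wound breakdown that communicates with the fracture or implant*.
2. State that any other breakdown counts as FRI only if criterion 2, 3 or 4 is met, and is otherwise recorded as a wound-healing problem. Infected breakdown that does not reach bone can then still count.
3. Have the existing adjudicators apply this wording when they vote on whether an event is a primary outcome.
4. Report FRI under the present wording as a sensitivity analysis.

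The cost is one phrase in the definition, one classification sentence, and one yes/no field for communication with the fracture or implant on the follow-up and reoperation forms. Adding the field now is worthwhile, since depth may be hard to recover later.

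There are downsides. Some judgements of depth in clinic will be uncertain, and the counted FRI rate may be somewhat lower. A purely mechanical breakdown that reaches the bone would still count. The sensitivity analysis will show how much the choice matters.
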